5.9 Changes to Planned Analyses

Any changes to the planned statistical analyses will be documented in an amended Statistical Analysis Plan approved prior to the change. Changes from the planned statistical methods after completion of the statistical analysis will be documented in the clinical study report along with a reason for the deviation

6 VALIDATION

All clinical data reports generated per this plan will be validated per 90702587, Global WI: Clinical Data Reporting Validation.

7 PROGRAMMING CONSIDERATIONS

7.1 Statistical Software

Statistical data review will be performed by the sponsor. Statistical analyses will be performed using SAS System software, version 9.2 or later (Copyright © 2000 SAS Institute Inc., [name]. All rights reserved).

7.2 Format of Output

Results of analysis will be output programmatically to Word documents from SAS with no manual intervention. All outputs for the final statistical reports will be in the form of a Word document containing tables, figures, graphs, and listings, as appropriate.

7.3 Rules and Definitions for Calculated Variables

Analysis approach:

7.3.1 Body Mass Index is calculated for each visit.

$$BMI = \frac{Weight(Kg) \times 10000}{(Height(cm))^2}$$

7.3.2 Stroke/TIA definitions

See protocol Sec.26

7.3.3 Classification of Bleeding events

See protocol Sec.26

7.3.4 Effective LAA closure rate

The subjects with LAA imaging at a given follow-up who have residual jet size ≤ 5 mm. The denominator is target samples at risk.

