ECHO Exclusion Criteria	
 1. The subject has LVEF < 30%. 2. The subject has intracardiac thrombus visualized by TEE within 2 days prior to implant. 3. The subject has an existing pericardial effusion with a circumferential echo-free space > 5mm, and/or the patient has signs/symptoms of acute or chronic pericarditis, and/or there is evidence (clinically or echocardiographically) of tamponade physiology. 4. The subject has a high- risk patent foramen ovale (PFO) with an atrial septal aneurysm excursion > 15mm or length \geq 15mm. 5. The subject has a high-risk PFO with a large shunt defined as early, within 3 beats, and/or substantial passage of bubbles. 6. The subject has significant mitral valve stenosis (i.e., MV < 1.5 cm²). 7. The subject has complex atheroma with mobile plaque of the descending aorta and/or aortic arch. 8. The subject has a cardiac tumor.
Multiple Interventions During Index Procedure	No concomitant procedures are to be performed at the time of the BSJ003W implant procedure. This includes, but is not limited to, cardiac ablation procedures, transcatheter valve procedures, cardioversions, pacemaker or ICD generator change, etc.
Statistical Methods	
Statistical consideration and Sample size justification	
The primary safety endpoint (endpoint1) event rate observed in the PREVAIL study was 2.2%. Based on the PREVAIL data only, the exact 95% upper confidence bound for this rate is 4.4%. An additional margin of 5.6% is added to this upper confidence bound to create a performance target of 10.0%. In order to maintain \geq95% probability that the observed estimate from this study is lower than the performance target of 10.0%, 40 subjects are required.
 
The expected primary effectiveness endpoint (endpoint3) rate is 99.3%. Based on this expected rate, and the number of subjects in the PREVAIL study with 6-month TEEs, the corresponding exact 95% lower confidence bound is 97.3%. An additional margin of 3.3% is subtracted from this lower confidence bound to create a

A study to confirm the safety and effectiveness of the BSJ003W in Japanese patients with non-valvular atrial fibrillation at increased risk of thromboembolism in Japanese clinical environment	
	performance target of 94.0%. Accounting for 10% attrition to 6-month TEE follow-up, 40 subjects are required to maintain $\geq 95\%$ probability that the observed estimate from this study is higher than the performance target of 94.0%.

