4 GENERAL STATISTICAL METHODS

4.1 Analysis Sets

The analysis set for the Co-Primary Endpoints analysis includes implanted subjects with a completed 6-month visit, i.e. for subjects who withdrawn consent/ missing before 6 month time window will be excluded from the implanted analysis set. The analysis set for the other analyses will be the "intent-to-treat" analysis set, including all implanted or attempted subjects.

Roll-in patients' data will be evaluated separately from the data of those patients enrolled after the Roll-in patients.

Intention-to-Treat (ITT) subjects are included in primary analysis for primary safety and efficacy endpoints as well as secondary endpoints and other endpoints. In addition, Implant subjects alone will be evaluated as needed as reference.

ITT: A subject who signs informed consent and regardless of the study device implanted or not, being enrolled into the study.

IMPLANT and ATTEMPT subjects are included in ITT.

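### SAP 4.1 names two incompatible primary sets for the co-primary endpoints, and 7.3.4 leaves the closure denominator undefined, so the pass/fail figures have no single fixed population

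*SAP*

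**What the plan says.** **Section 4.1, first paragraph.** "The analysis set for the Co-Primary Endpoints analysis includes implanted subjects with a completed 6-month visit". Subjects who withdraw or go missing before the 6-month window are excluded. ITT is kept for everything else: "The analysis set for the other analyses will be the" intent-to-treat set, described there as implanted or attempted subjects.

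**Section 4.1, later paragraphs.** "Intention-to-Treat (ITT) subjects are included in primary analysis for primary safety and efficacy endpoints", and the implanted set becomes secondary: "Implant subjects alone will be evaluated as needed as reference". ITT is now defined by consent and enrolment, "regardless of the study device implanted or not, being enrolled into the study".

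**Section 7.3.4.** The numerator is "The subjects with LAA imaging at a given follow-up who have residual jet size" of at most 5 mm. Then: "The denominator is target samples at risk". The SAP does not define that term. Unlike 7.3.2 and 7.3.3, this entry does not refer to the protocol.

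**Decision rule and sizing.** Section 3 says the objectives are met only if both the safety target (10%) and the efficacy target (94%) are met. No hypothesis is tested. Sections 1 and 3.2.2 compare the observed closure rate with 94.0%, allow 10% attrition to the 6-month TEE and tolerate up to 2 subjects not closed. The lower bound behind the target in section 1 rests on "the number of subjects in the PREVAIL study with 6-month TEEs".

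**Section 5.6.** Worst-case and tipping-point analyses are described for missing primary outcomes, with the tipping point on the ITT set. The opening sentence makes the sensitivity analyses conditional on need.

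**The concern.** The two statements in 4.1 cannot both define the primary analysis, and nothing ranks one above the other. They differ on attempted-but-not-implanted subjects and on subjects without a completed 6-month visit. The two descriptions of ITT add a further ambiguity, since a subject who consented and was enrolled but never reached an implant attempt fits only the second.

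The conflict covers all three co-primary endpoints. For Endpoint 1, requiring a completed 6-month visit can remove attempted-only subjects and subjects who died early, although all-cause death is itself an Endpoint 1 event. For Endpoint 3, the endpoint definition should fix the denominator and does not.

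The targets are judged on point estimates in about 36 to 40 subjects, so one or two subjects can move the result across the line. If the set is not fixed in advance, it could be chosen after the data are seen.

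**Working it through.** **Inputs.** N = 40, 10% attrition to the 6-month TEE, expected closure 99.3%, pass if the observed rate is above 94.0% (sections 1 and 3.2.2). The number of failed implants, f, is not given in the SAP; I assume 0 to 3.

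**1. The SAP's own figure.** 40 × 0.90 = 36 imaged subjects. 34/36 = 94.4% passes and 33/36 = 91.7% fails, so 2 failures are allowed. P(Bin(36, 0.007) ≤ 2) = 0.998. The stated probability of at least 95% and the allowance of 2 failures both reproduce on imaged subjects.

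**2. Conditional illustration for Endpoint 3.** With f failed implants and 10% attrition among the other 40 − f, about 36 − f subjects have a TEE after rounding.

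- *ITT reading:* failed implants count as not closed and missing TEEs are dropped. The denominator is (36 − f) + f = 36, so 34 closures are needed: P(Bin(36 − f, 0.993) ≥ 34).
- *Imaged reading:* the denominator is 36 − f. Up to 2 failures are allowed at n = 36, 35 and 34 (32/34 = 94.1%), but only 1 at n = 33 (32/33 = 97.0% passes, 31/33 = 93.9% fails).

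| Failed implants (assumed) | ITT: P(pass) | ITT: best possible rate | Imaged: n | Imaged: P(pass) |
|---|---|---|---|---|
| 0 | 0.998 | 36/36 = 100% | 36 | 0.998 |
| 1 | 0.975 | 35/36 = 97.2% | 35 | 0.998 |
| 2 | 0.788 | 34/36 = 94.4% | 34 | 0.998 |
| 3 | 0 | 33/36 = 91.7% | 33 | 0.978 |

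With 3 failed implants and all 33 imaged subjects closed, the same data give 33/33 = 100% or 33/36 = 91.7%.

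**3. Outer bound.** If all 40 stay in the denominator, and failed implants and unimaged subjects alike count as not closed, then 38/40 = 95.0% passes and 37/40 = 92.5% fails. With m = 0, 1, 2, 3 such subjects, P(Bin(40 − m, 0.993) ≥ 38) = 0.997, 0.969, 0.766, 0.

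**4. Endpoint 1, hypothetical counts.** With 40 subjects, 3/40 = 7.5% is below the 10% target and 4/40 = 10.0% is not. If one of 4 events is an early death, and that subject is excluded for lack of a completed 6-month visit, the rate becomes 3/39 = 7.7% and the target is met.

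**The case against.** The strongest reply is that the intended closure denominator can be inferred. The benchmark rests on subjects with 6-month TEEs, the sizing deducts TEE attrition, the numerator in 7.3.4 is imaged subjects, and 5.6 treats missing outcomes as a sensitivity matter. On that reading the sample-size claim holds. This stands as evidence of intent. But no section states it as the rule, and the imaged set is neither of the two sets in 4.1: an implanted subject who attends at 6 months without a readable TEE belongs to the first-paragraph set but not to the imaged one.

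Second, the reversal in the table needs a scoring rule that the SAP does not contain. Closure is defined by peri-device flow on TEE, so a subject without a device may be read as simply not assessable. If failed implants are dropped along with other unimaged subjects, the ITT and imaged rates coincide. Section 3.2.2 leans the other way, since its allowance of 2 covers subjects not closed for whatever reason. The point is arguable and should be written down.

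Third, 5.6 already plans worst-case and tipping-point work on ITT. That is true, but it does not choose the primary set, and its opening sentence makes the sensitivity analyses conditional.

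A reader might also infer that the planned 10% attrition alone makes the target unreachable, because 36/40 = 90.0%. The SAP does not support this. It requires counting every missing TEE as not closed in the primary analysis, whereas the sizing allows for that attrition.

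**Conclusion.** The contradiction in 4.1 and the undefined denominator in 7.3.4 are on the page and need no assumption. They bear on figures that section 3 makes decisive, so they should be resolved before analysis.

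The size of the effect on Endpoint 3 is conditional. It rests on a true closure rate of 99.3%, 10% TEE attrition, an assumed 0 to 3 failed implants, and failed implants counting as not closed. Under those assumptions the ITT probability stays above 95% with 0 or 1 failed implant, falls to 0.788 with 2 and is 0 with 3. With no failed implants the two readings agree.

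It would go too far to conclude that the sample size is wrong or that the result will turn on the choice of set. The stated probability reproduces on imaged subjects, and the SAP gives no implant-failure rate. For Endpoint 1 the concern is the possible loss of early deaths and attempted-only subjects. The wording of 4.1 permits this without expressly saying how deaths are handled.

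**What to change.** - **4.1:** Delete the first-paragraph sentence that restricts the co-primary set to implanted subjects with a completed 6-month visit. Keep a single ITT definition.
- **Endpoints 1 and 2:** Analyse all non-roll-in ITT subjects (implanted or attempted), so that early deaths and attempted-only subjects stay in.
- **Endpoint 3, in 7.3.4:** Replace the sentence "The denominator is target samples at risk" with one explicit denominator, and say how an attempted-but-not-implanted subject and a missing or unreadable 6-month TEE count. Two choices are coherent: non-roll-in subjects with an evaluable core-lab TEE at the visit, which is the sizing basis; or ITT, with the probability of at least 95% restated on that basis.
- **5.6:** Drop the *if necessary* qualifier for this endpoint, so that the ITT worst-case and tipping-point results always accompany the primary closure rate.

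The cost is SAP wording and a little extra analysis, with no new data. The reported closure rate or the stated probability may look slightly less favourable. If the evaluable-TEE set is chosen, the primary rate is complete-case and leaves out failed implants; the mandatory ITT worst-case result offsets that.

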7.3.5 Time in Therapeutic range (TTR)

To explore appropriateness of Warfarin control and/or explore the relationship between bleedings, TTR is calculated by Rosendaal Method. (under linear assumption of INR change, then percentage of total of “within therapeutic range time “out of “Time between visits” is calculated.)

The normal ranges of INR are refer to 2.0-3.0 for age less than 70 years, and to 1.6-2.6 for age 70 years old or older in accordance with JCS guideline, and also for a subject 70 years old or older, a recommended range is to 2.0-2.6 in SALUTE protocol consideration.

End of file

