1 PROTOCOL SUMMARY

A study to confirm the safety and effectiveness of the BSJ003W in Japanese patients with non-valvular atrial fibrillation at increased risk of thromboembolism in Japanese clinical environment	
Study Objective(s)	To confirm the safety and effectiveness of the BSJ003W in Japanese patients with non-valvular atrial fibrillation at increased risk of thromboembolism in Japanese Clinical environment
Planned Indication(s) for Use	To reduce the risk of thromboembolism from the Left Atrial Appendage in patients with non-valvular atrial fibrillation who are at increased risk based on CHADS ₂ or CHA ₂ DS ₂ -VASc scores
Test Device	BSJ003W LAA Closure Technology; three-component system consisting of the 
 • BSJ003W Closure Device; WATCHMAN(Gen 2.5) • BSJ003W Delivery System (Delivery Catheter and BSJ003W Closure Device) • BSJ003W Access System (Access Sheath and Dilator)
Control Device	None
Device Sizes	21mm, 24mm, 27mm, 30mm, 33mm
Study Design	This is a prospective, multi-center, single-arm study to confirm the safety and effectiveness of BSJ003W for Japanese subjects with non-valvular atrial fibrillation who are eligible for long-term anti-coagulation therapy to reduce the risk of stroke but who have a rationale to seek a non-pharmacologic alternative in Japanese clinical environment.
Planned Number of Subjects	One Roll-in subject per site is required prior to enroll an analyzable subject at each site. One more Roll-in subject should be enrolled if necessary per Investigators' or a proctor's discretion. Number of analyzable patients: 40 patients. Maximum of 60 subjects (including 10-20 Roll-in subjects) will be enrolled in the study.
Planned Number of Investigational Sites	Up to 10 investigational centers in Japan

A study to confirm the safety and effectiveness of the BSJ003W in Japanese patients with non-valvular atrial fibrillation at increased risk of thromboembolism in Japanese clinical environment

Primary Endpoints

To assess safety and effectiveness of BSJ003W, the following three endpoints are established as Co-Primary Endpoints:

1. The occurrence of one of the following events between the time of implant and within 7 days following the procedure or by hospital discharge, whichever is later:

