Additional Endpoints	
Device performance:
 
 • Technical Success defined as successful delivery and release of BSJ003W into the LAA including successful recapture and retrieval if necessary. 
Safety endpoints:
 
 • Occurrence of reportable adverse events • Occurrence of all-cause mortality 
Effectiveness endpoints:
 
 • Individual occurrence of all-cause death, ischemic stroke,

A study to confirm the safety and effectiveness of the BSJ003W in Japanese patients with non-valvular atrial fibrillation at increased risk of thromboembolism in Japanese clinical environment									
	
hemorrhagic stroke, systemic embolization, cardiovascular death (including unexplained cause) at 6-month, 12-month and 24-month.
 
 • Warfarin discontinuation rate at 45 days, 6-month and 12-month • Severity of stroke assessed by NIH Stroke Score, Modified Rankin Scale Score, and Barthel Index 
Other endpoint:
 
 • EQ-5D 								
Required Medication Therapy	
  
 Visit	Medication	
   
 Implant through 45-day visit	ASA+ Warfarin	
 
 45-day visit through 6-month visit	ASA+ Thienopyridine	
 
 Following the 6-month visit	ASA	
  
 
Warfarin therapy should be appropriately monitored and adjusted so as to achieve a therapeutic INR of 2.0- 3.0. For a subject who are 70 years old or older, a therapeutic INR of 2.0 – 2.6 is recommended considering the high risk of major bleeding. Subjects should remain on warfarin until the 45-day TEE evaluation has shown adequate seal of the LAA. If the LAA is not adequately sealed, the subjects should be on warfarin and Aspirin therapy.
	Visit	Medication	Implant through 45-day visit	ASA+ Warfarin	45-day visit through 6-month visit	ASA+ Thienopyridine	Following the 6-month visit	ASA
Visit	Medication								
Implant through 45-day visit	ASA+ Warfarin								
45-day visit through 6-month visit	ASA+ Thienopyridine								

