5.8 Other Analyses

- To explore the relationship between LAA closure rate and other endpoints, effective LAA closure rate at 45 days and 6 months will be used to classified other endpoints.
- Descriptive analysis will be used for other analysis.
- To explore the relationship between all bleedings, the descriptive of TTR (Time in Therapeutic Range), and an appropriate correlation of bleeding rate and TTR are calculated.

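### SAP 7.3.5 lists two unreconciled INR ranges for TTR from age 70, and 5.8 plans a bleeding-TTR correlation without adjustment for age; on the narrower range, a pooled correlation can turn modestly negative through age alone

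*SAP*

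**What the plan says.** Section 7.3.5 states that "TTR is calculated by Rosendaal Method" and sets the INR range by age. Below 70: "The normal ranges of INR are refer to 2.0-3.0 for age less than 70 years". From 70 the same sentence gives two ranges. The first is "to 1.6-2.6 for age 70 years old or older in accordance with JCS guideline". The second follows directly: "for a subject 70 years old or older, a recommended range is to 2.0-2.6 in SALUTE protocol consideration". Nothing says which of them defines in-range time for the older group, or whether TTR is to be computed under both.

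The protocol summary in section 1 (Required Medication Therapy) repeats the second range and gives a reason: "a therapeutic INR of 2.0 – 2.6 is recommended considering the high risk of major bleeding".

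Section 5.8 uses TTR to explore all bleeding events. Besides descriptive statistics of TTR, "an appropriate correlation of bleeding rate and TTR are calculated". The type of correlation is not named, and age is not mentioned.

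**The concern.** Age 70 decides which range a subject's TTR is scored on. The SAP also links age 70 or older to a high risk of major bleeding. A variable that may move both sides of a correlation, and is left out of it, is a confounder. Here part of its effect on TTR would come from the definition of TTR and not from the quality of INR control.

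On 2.0-2.6, an older subject with the same INR stability as a younger one gets a lower TTR because the target is narrower. If older subjects also bleed more, the pooled correlation can look like worse control going with more bleeding when it only separates two age groups. TTR is calculated in order to explore warfarin control and its relation to bleeding, so this would mislead on the question it is meant to answer.

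The open choice of range adds to this. Two analysts following 7.3.5 could score the older subjects differently and obtain different TTRs and different correlations from the same data.

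**Working it through.** The SAP states no expected TTR, correlation or error rate for this analysis, so there is no figure of its own to reproduce.

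**Step 1: widths of the listed ranges (7.3.5).**
- Below 70: 3.0 - 2.0 = 1.0
- From 70, guideline range: 2.6 - 1.6 = 1.0
- From 70, trial's recommended range: 2.6 - 2.0 = 0.6

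The two ranges for the older group share the upper limit of 2.6. They differ only in whether INR between 1.6 and 2.0 counts as in range.

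**Step 2: expected time in range at equal INR stability.** Assumed, as the SAP gives no INR distribution: INR is normal with the same SD in both groups, mean 2.5 below 70 and mean 2.3 from 70. The formula is Φ((upper - mean)/SD) - Φ((lower - mean)/SD).

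| SD | <70, 2.0-3.0 | >=70, 2.0-2.6 | gap (points) | >=70, 1.6-2.6 | gap (points) |
|---|---|---|---|---|---|
| 0.3 | 90.4% | 68.3% | 22.1 | 83.2% | 7.2 |
| 0.5 | 68.3% | 45.1% | 23.2 | 64.5% | 3.8 |
| 0.7 | 52.5% | 33.2% | 19.3 | 50.7% | 1.8 |

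For SD 0.5, for example, the first gap is [Φ(1) - Φ(-1)] - [Φ(0.6) - Φ(-0.6)] = 0.683 - 0.451. If the older group's mean is 2.1 instead, TTR at SD 0.5 is 42.1% on 2.0-2.6 and 68.3% on 1.6-2.6, so the gap is 26.2 points on the first range and zero on the second.

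**Step 3: effect on a pooled correlation.** Simulated: 40 subjects (the planned analysable number), TTR by linear interpolation over 6 INR readings, SD 0.5 within and 0.2 between subjects, bleeding dependent on age group only. Any average correlation other than zero is therefore spurious. The share aged 70 or older, the bleeding rate and the ratio between age groups are assumptions.

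- Scored on 2.0-2.6, with 0.3 bleeds per younger subject, 50-90% aged 70 or older and bleeding ratio 2-3: mean Spearman correlation about -0.05 to -0.19.
- Within that setting, with half the subjects aged 70 or older: -0.11 at ratio 2 and -0.18 at ratio 3, negative in 76% and 88% of runs, and p<0.05 in 9% and 21%. With 75% aged 70 or older: -0.08 and -0.14.
- With fewer bleeds (a yes/no outcome at 10% risk below 70, ordinary correlation coefficient, shares 50-90%): -0.02 to -0.08 at ratio 2 and -0.04 to -0.14 at ratio 3. The sign is not negative in roughly 18-43% of runs.
- Scored on 1.6-2.6: about -0.01 to -0.04 in the first setting and -0.03 to +0.01 in the setting with fewer bleeds.
- At bleeding ratio 1: about zero on either range.

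**Step 4: check of the remedy.** A rank correlation adjusted for age group (<70, >=70) averages -0.01 to +0.01 in every scenario.

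**The case against.** The strongest objection is that the SAP does not fix the narrower range. The first range that 7.3.5 gives for the older group is as wide as the one for the younger group, and on it the artefact nearly vanishes. This stands. A reader might infer that TTR is scored on a narrower range from age 70 and that a negative correlation therefore follows by construction. The SAP does not support that. The effect needs both the 2.0-2.6 reading and a real age difference in bleeding, and even then the sign is not assured with 40 subjects.

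A second objection is that the age difference is assumed. The protocol summary speaks of major bleeding and gives no rate or ratio, while 5.8 covers all bleeding. This also stands, and it is why the result is given as a range that includes the null case.

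Third, 5.8 asks for an appropriate correlation, which leaves room for a stratified or adjusted one. It does, but it does not ask for either. Age appears in the subgroups of 5.3 and the covariates of 5.5, but with a cut at 75 and without TTR, so those analyses do not deal with the point.

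Finally, the analysis is exploratory, with no hypothesis or decision attached. That limits the weight of the point but does not remove it, since the remedy costs almost nothing.

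**Conclusion.** The point holds in a limited form. Section 7.3.5 leaves TTR undefined from age 70 by listing two ranges without choosing between them for scoring, and 5.8 plans a correlation with bleeding that is not adjusted for the age group that sets the range. On 2.0-2.6, and if older subjects bleed two to three times as often, a pooled correlation is biased by about -0.05 to -0.19 on average under the assumptions above, and by less if bleeding is rarer. On 1.6-2.6, or without an age difference in bleeding, the bias is close to zero.

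The bias is modest and affects one exploratory analysis. No primary endpoint is touched. It is a cheap improvement and not a flaw in the trial's conclusions. Nothing here bears on which INR range is clinically right.

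**What to change.** - **Section 7.3.5:** reconcile the two ranges listed from age 70 by stating which one is used to score TTR, or state that TTR will be reported under both. This is a scoring definition only and takes no view on clinical targets.
- **Section 5.8:** calculate the bleeding-TTR correlation as a partial rank correlation adjusted for age group (<70, >=70), or separately within those two groups, in place of a correlation pooled over subjects scored on different ranges.

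The cost is a sentence or two in each section and minor programming. No new data are needed, because 7.3.5 already uses this age group to set the range. The downside is slightly less precision, and more so if about 40 subjects are split into strata, so the adjusted form is the more economical of the two.
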